Appendix C – Birth Control Methods that May Be Considered as Highly Effective

Methods that can achieve a failure rate of less than 1% per year when used consistently and correctly are considered as highly effective birth control methods. Such methods include:

- combined (estrogen and progestogen containing) hormonal contraception associated with inhibition of ovulation 1:
 - oral
 - intravaginal
 - transdermal
- progestogen-only hormonal contraception associated with inhibition of ovulation 1:
 - oral
 - injectable
 - implantable
 - intrauterine device (IUD)
 - intrauterine hormone-releasing system (IUS)
 - bilateral tubal occlusion
 - vasectomized partner
 - sexual abstinence

Guidance on the acceptable contraception methods can be found here:

http://www.hma.eu/fileadmin/dateien/Human_Medicines/01-About_HMA/Working_Groups/CTFG/2014_09_HMA_CTFG_Contraception.pdf

Appendix D – RECIST v.1.1 Criteria

The primary efficacy endpoint is ORR. Tumor response will be assessed by RECIST v.1.1 guidelines on images obtained with CT scans. CT scans will be performed at Baseline during Screening (within 4 weeks prior to Day 1), at Week 9 (± 7 days) and every 9 weeks (± 7 days) during the study treatment and during the first year from discontinuation of the study treatment, every 12 weeks (± 7 days) during the second year, and every 16 weeks (± 7 days) thereafter. Tumor assessment will be repeated until disease progression, death, or receipt of new anti-cancer therapy, or until study completion, whichever is first, whether or not study treatment was administered. Radiologic studies for antitumor response will be repeated at the end of treatment visit only if required per the defined study imaging schedule.

Definition of Measurable and Non-Measurable Lesions

Measurable Lesions at Baseline

The definition of a measurable lesion at Baseline is dependent on the technical factors of the imaging studies that were used to evaluate the patient. The recommendations for the imaging parameters are based on the American College of Radiology (ACR) Practice Guidelines and Technical Standards. The ACR Practice Guidelines and Technical Standards define principles and technical parameters of radiologic and radiation oncology practice, which should generally produce desired health care outcomes. They describe a range of acceptable approaches for the diagnosis and/or treatment of disease for most patients, in most circumstances. Given differences in training, experience, and local conditions, the ACR Practice Guidelines and Technical Standards acknowledge the need for health care providers to exercise their independent medical judgment in making decisions regarding the use and specific details of any procedure.

For CT scanning, the recommendation is for a slice thickness of 5 mm or less.

The RECIST v.1.1 guideline recommends CT images for chest, abdomen, and pelvis should be performed using 5 mm reconstructions, but it is not explicitly stated as a requirement ([Eisenhauer, Therasse et al. 2009](#)).

In preparing the technical specifications, we have followed the guidelines of the ACR, as 5 mm reconstructions are not the standard in the US or the rest of the world. Our proposal for modifying the size of measurable lesions at Baseline to 2 times the reconstruction interval of the Baseline/Screening studies is consistent with the RECIST definition for a measurable lesion.

- Conventional CT should be performed with contiguous cuts of 10 mm or less in reconstruction interval. CT should be performed by use of a 5–8 mm contiguous reconstruction interval or less, where the neck and brain CTs should be done at 5 mm or less.
- Lesions that can be accurately measured in at least 1 dimension with the longest diameter (LD) ≥ 20 mm with conventional techniques when the conventional scans are performed with a reconstruction interval of 10 mm or less are measurable lesions.

- Lesions that can be accurately measured in at least 1 dimension with the LD being 2 times the reconstruction interval (RI) of the CT scan. Depending on the RI of the CT (5–8 mm or less recommended) measurable lesion size may be $\geq 10\text{--}16$ mm. For example, a CT scan done at 8 mm RI would have a minimum lesion size of 16 mm in the longest dimension. The minimum size of a measurable lesion is 10 mm.
- Although initially identified as measurable lesion ≥ 10 mm, target lesions may in time reduce to <5 mm in their LD. In those circumstances where the target lesion LD is less than the 5 mm minimum for measurability, the lesion LD should be recorded as 5 mm.
- In the instance where the reconstruction interval has changed from the Baseline to subsequent time points, it would be at the discretion of the radiologist whether this would affect interpretation. A note is made in the comment section of the source document, if applicable. The definition for target disease would not change and would be determined on the basis of the Baseline scan.

Non-Measurable Lesions

All other lesions that do not meet the criteria for measurable disease as well as other truly non-measurable lesions (eg, ascites, bone lesions, pleural effusion, etc.), are considered non-measurable.

Definition of Target, Non-Target and New Lesions (RECIST v1.1 Guidelines)

Target Lesions

Up to 5 target lesions, a maximum of 2 per organ, will be chosen for measurement over the course of the study. The distribution of these target lesions should be representative of the patient's overall disease. Target lesions should not be chosen from a previously irradiated area unless lesions in those areas have documented progression.

Target lesions must be measurable at Baseline. These lesions will generally be the largest lesions, most reliably measured, and most representative of the patient's sites of disease.

For any target lesion at any time point, measurements will be taken and recorded unidimensionally. The longest dimension of each target lesion will be measured and recorded. The longest dimension of the target lesions will be summed to obtain the Sum of the Longest Diameters (SLD). The Baseline SLD will be used as reference to further characterize the objective tumor response of the target lesions. For the consideration of progressive disease, the nadir of the SLD for the target lesions will be used as reference.

For cases where there is no target lesion identified, tumor assessment for progression should be done based on non-target lesion assessments or the development of new lesions.

Response (PR or CR) and SD will not be assessed in patients where target lesions are not identified at Baseline. The following conventions will be applied in selecting target lesions in patients who have received prior radiation therapy:

- Intrathoracic measurable lesions in the periphery of the lung, just deep to the radiated chest wall concordant with the radiation portal cannot be selected as target lesions. However, if the lesions are more centrally located in the chest and do not appear in regions showing evidence of radiation injury (eg, scarring, radiation pneumonitis, etc.),

they can be selected as target lesions. The assigned radiologist will document descriptions of radiation damage in the comments field.

- Prior bone radiation (eg, vertebral, rib, pelvis, femur, etc., as stated on the Prior Radiation Therapy Form would not preclude the selection of measurable lesions in adjacent structures unless signs of radiation injury are evident (eg, scarring).
- Prior soft tissue radiation (eg, supraclavicular radiation, radiation of internal mammary lymph nodes, etc., as recorded on the Prior Radiation Therapy Form would preclude the selection of measurable disease in the site of radiation unless the site confirms on the Prior Radiation Therapy Form that the lesions are new since radiation was completed.

Non-Target Lesions

All of the sites of disease present at Baseline not classified as target lesions will be classified as non-target lesions. Non-target lesions must be qualitatively assessed at each subsequent time point. Examples of non-target lesions include:

- All bone lesions, irrespective of the modality used to assess them;
- Leptomeningeal disease;
- Lymphangitis of the skin or lung;
- Cystic lesions;
- Irradiated lesions that have not shown progression;
- Measurable lesions beyond the maximum number of 10;
- Groups of lesions that are small and numerous; and
- Pleural effusion/pericardial effusion/ascites.

New Lesions

Unequivocal new lesions are those that were not present at Baseline. At each time point, the presence of new lesions will be determined. New multi-focal or miliary disease of any size is considered a new lesion.

Lesions that are encountered (subsequent to the Baseline) in anatomic locations that were not scanned at Baseline will be considered new lesions and will represent progressive disease.

Lesions that were present which subsequently resolved and then recurred will be considered new lesions and will represent progressive disease.

Antitumor Response (RECIST v1.1 Guidelines)

Antitumor response will be defined as the percent of patients who achieve an objective confirmed response (complete or partial response). Disease control rate (SD for at least 16 weeks or confirmed CR or PR) also will be reported. Response will be determined according to RECIST guidelines. The original RECIST guidelines were developed and published in the Journal of the National Cancer Institute ([Therasse, Arbuck et al. 2000](#)).

Target Lesion Response (RECIST v1.1 Guidelines)

Percentage change in SLD will be evaluated by the following formulae:

1. When determining complete response or partial response:

$$(\text{Post value} - \text{Baseline value}) / \text{Baseline value} \times 100$$

2. When determining progressive disease:

$$(\text{Post value} - \text{Nadir value since treatment started}) / (\text{Nadir value since treatment started}) \times 100$$

The following definitions will be used to evaluate response based on target lesions at each time point after Baseline:

Complete Response (CR): Disappearance of all target lesions.

Partial Response (PR): At least a 30% decrease in the SLD of target lesions, taking as reference the Baseline SLD.

Stable Disease (SD): Neither sufficient shrinkage of target lesions to qualify for PR, nor sufficient increase to qualify for PD, taking as reference the nadir SLD since the treatment started.

Progressive Disease (PD): At least a 20% increase in the SLD of target lesions, taking as reference the nadir SLD recorded since the treatment started, or, the presence of one or more new lesions. In addition to the relative increase of 20%, the sum must also demonstrate an absolute increase of at least 5 mm. The appearance of one or more new lesions is also considered progression. PET scans will not be used to determine target lesion progression or as a criterion for patient withdrawal from the study. Only CT scans or MRIs will be used for those purposes.

Not evaluable (NE): A target lesion present at Baseline which was not measured or which was unable to be evaluated leading to an inability to determine the status of that particular tumor for the time point in question. If the SLD cannot be determined at a time point and the rules for PD do not apply, a response of CR, PR, or SD cannot be assigned for that time point, and the time point response will be NE.

Not Applicable (NA): No target lesions were identified at Baseline. Patients with no target lesions identified at Baseline cannot be assessed for response. These patients will be assessed for progression only.

Not Done (ND): Scans were not performed at this time point to evaluate the target lesions.

Non-Target Lesion Response (RECIST v1.1 Guidelines)

Each non-target lesion will be qualitatively evaluated at each time point. Response of each lesion at each time point will be assessed with respect to the Baseline status. Progression will be assessed with respect to nadir size of the non-target lesions. The overall non-target lesion response for each time point will be assessed as the worst case for the non-target

lesions for that particular time point. If a non-target lesion is classified as NE/ND, the non-target response will be NE/ND unless progression is identified in the available non-target lesions. Response assessments are defined as follows:

Complete Response (CR): Disappearance of all non-target lesions, and normalization of tumor marker level. All lymph nodes must be non-pathological in size (<10 mm short axis)
Non-CR / Non-PD: Persistence of one or more non-target lesions and or maintenance of tumor marker level above the normal limits.

Progressive Disease (PD): The “unequivocal progression” of existing non-target lesion(s) or appearance of one or more new lesion(s) is considered progressive disease.

Not Evaluable (NE): Any non-target lesion present at Baseline which was not measured or was unable to be evaluated leading to an inability to determine the status of that particular tumor for the time point in question.

Not Applicable (NA): No non-target lesions were identified at Baseline.

Not Done (ND): Scans were not performed at this time point to evaluate the non-target lesions.

Pseudoprogression: Patients whose scans show radiographic progression in the absence of clinical deterioration including worsening performance status as assessed by the Investigator may remain on study treatments and additional scan 4 weeks (± 7 days) later. If this subsequent scan shows disease progression, the patient will be discontinued from study treatments.

Response Determination (RECIST v1.1 Guidelines)

Response at each time point will be assessed as a combination of the target and non-target responses as well as the presence of new lesions according to the table below:

Time Point Response / Target and Non-Target and Best Response

Target

Time Point Response: Patients With Target (\pm Non-Target) Disease			
Target Lesions	Non-Target Lesions	New Lesions	Overall Response
CR	CR	No	CR
CR	Non-CR/non-PD	No	PR
CR	Not evaluated	No	PR
PR	Non-PD or not all evaluated	No	PR
SD	Non-PD or not all evaluated	No	SD
Not all evaluated	Non-PD	No	NE
PD	Any	Yes or No	PD
Any	PD	Yes or No	PD
Any	Any	Yes	PD

CR = complete response, PR = partial response, SD = stable disease,

PD = progressive disease, and NE = not evaluable

Non-Target

Time Point Response: Patients With Non-Target Disease Only		
Non-Target Lesions	New Lesions	Overall Response
CR	No	CR
Non-CR/non-PD	No	Non-CR/non-PD*
Not all evaluated	No	NE
Uequivocal PD	Yes or No	PD
Any	Yes	PD

CR = complete response, PD = progressive disease, and NE = not evaluable

* “Non-CR/non-PD is preferred over “stable disease” for non-target disease since SD is increasingly used as endpoint for assessment of efficacy in some trials so to assign this category when no lesions can be measured is not advised.

Best Overall Response – Confirmation of CR and PR

Best Overall Response When Confirmation of CR and PR Required		
Overall Response First Time Point	Overall Response Subsequent Time Point	Best Overall Response
CR	CR	CR
CR	PR	SD, PD or PR*
CR	SD	SD provided minimum criteria for SD duration met, otherwise, PD
CR	PD	SD provided minimum criteria for SD duration met, otherwise, PD
CR	NE	SD provided minimum criteria for SD duration met, otherwise, NE
PR	CR	PR
PR	PR	PR
PR	SD	SD
PR	PD	SD provided minimum criteria for SD duration met, otherwise, PD
PR	NE	SD provided minimum criteria for SD duration met, otherwise, NE
NE	NE	NE

CR = complete response, PR = partial response, SD = stable disease, PD = progressive disease, and NE = not evaluable

*If a CR is truly met at first time point, then any disease seen at a subsequent time point, even disease meeting PR criteria relative to baseline, makes the disease PD at that time point (since, disease must have reappeared after CR). Best response would depend on whether minimum duration for SD was met. However, sometimes 'CR' may be claimed when subsequent scans suggest small lesions were likely still present and in fact the patient had PR, not CR at the first time point. Under these circumstances, the original CR should be changed to PR and the best response is PR.

Source: [\(Eisenhauer, Therasse et al. 2009\)](#).

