7.11 Laboratory Assessments

Local laboratories will perform the following laboratory tests, and results will be provided to the Investigator. Blood and urine samples for hematology, chemistry, activated partial thromboplastin (aPTT) and International Normalized Ratio (INR) or Prothrombin (PT), thyroid function, and urinalysis will be prepared using standard procedures. Laboratory panels are defined as follows:

Hematology	WBC count with differential, RBC count, hemoglobin, hematocrit, reticulocyte count, and platelet count
Chemistry	albumin, ALP, ALT, AST, BUN, calcium, carbon dioxide, chloride, creatinine, glucose, potassium, sodium, total bilirubin, lactate dehydrogenase, and total protein
Coagulation Tests:	aPTT and International Normalized Ratio (INR) or PT
Thyroid Function Test	TSH, free T3, and free T4
Urinalysis	appearance, color, pH, specific gravity, ketones, protein, glucose, bilirubin, nitrite, urobilinogen, and occult blood (microscopic examination of sediment will be performed only if the results of the urinalysis dipstick evaluation are positive)
Pregnancy Test	Serum or urine pregnancy test for women of child bearing potential

Abnormalities in clinical laboratory tests that lead to a change in patient management (ie, dose withhold or modification, requirement for additional medication or monitoring) are considered clinically significant for the purposes of this trial and will be recorded on the AE CRF page. If values meet criteria defining them as serious, they must be reported as SAEs (Section 9.1.2).

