#### **6.5.3.4. Duration of Response**

Duration of response is defined as the time from the date of first documentation of objective tumor response criteria for CR or PR (whichever is first recorded) to the date of the first documentation of tumor progression (clinical progression or progression per scans) or death due to any cause, whichever occurs first. If a patient does not progress following a response, then their duration of response will use the PFS censoring time.

The analysis of response duration will only include ITT patients with CR or PR. Duration of response will be summarized with descriptive statistics (median and 95% CI) for each treatment arm using the Kaplan-Meier method.

Duration of CR is defined as the time from the date of first documentation of objective response criteria for CR to the date of documentation of tumor progression (clinical progression or progression per scans) or death, whichever occurs first.

Duration of SD is defined as the time from randomization until the criteria for progression are met (clinical progression or progression per scans or death, whichever occurs first).

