##### **6.5.4.3. Change in Tumor Burden**

Percentage change from baseline in tumor burden will be calculated at each tumor assessment. Best percentage change from baseline in tumor burden will be calculated as the biggest decrease or the smallest increase in tumor burden from baseline.

Tumor burden is defined as the sum of the longest diameters of the target lesions (the measurable tumor lesions).

The percentage change from baseline in tumor burden is calculated as:  $(\text{Sum of target lesions at week } x - \text{sum of target lesions at baseline}) / \text{sum of target lesions at baseline} * 100$

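### Appendix D gives no 0 mm entry for a vanished target lesion and ties non-target CR to an unmeasured tumor marker, so some PRs can be scored SD and some cleared patients fit no category

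*Protocol*

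**What the plan says.** **Target lesions (Protocol Appendix D).** At baseline, "The minimum size of a measurable lesion is 10 mm". "Up to 5 target lesions, a maximum of 2 per organ", are followed. For a lesion that later shrinks, the rule is: "where the target lesion LD is less than the 5 mm minimum for measurability, the lesion LD should be recorded as 5 mm". No value is given for a lesion that can no longer be seen. The percentage change from the baseline sum of longest diameters (SLD) is introduced with the words "When determining complete response or partial response". PR is a fall in SLD of at least 30% from baseline. PD is a rise of at least 20% and 5 mm from the nadir SLD, or a new lesion. Target CR is defined by disappearance of all target lesions, with no SLD value attached.

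**Non-target lesions (same appendix).** CR requires "Disappearance of all non-target lesions, and normalization of tumor marker level". It also requires lymph nodes of non-pathological size. Non-CR/Non-PD requires a persisting lesion, a marker that stays above normal, or both.

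**What is measured.** The chemistry panel in Protocol 7.11 is "albumin, ALP, ALT, AST, BUN, calcium, carbon dioxide, chloride, creatinine, glucose, potassium, sodium, total bilirubin, lactate dehydrogenase, and total protein". No panel in 7.11, nor the Appendix A schedule, lists a tumor marker. The blood samples in 7.14 are exploratory, with no tumor marker or normal limit named. Lactate dehydrogenase is measured, but nothing designates it as the marker meant.

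**Where the scores are used.** SAP 6.5.2.1 counts CR and PR alike in the investigator-assessed primary ORR; ORR5 repeats the analysis on independent review. SAP 6.5.4.1 reports CR as its own best-response category. SAP 6.5.3.4 adds: "Duration of CR is defined as the time from the date of first documentation of objective response criteria for CR". SAP 6.5.4.3 states: "Tumor burden is defined as the sum of the longest diameters of the target lesions".

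**The concern.** PR depends on a number, so a lesion that has gone needs a recorded value whenever other target lesions remain. If 5 mm is carried forward, the SLD overstates the remaining tumor. That moves the PR call, and with it the primary endpoint. It also moves the nadir against which PD is judged. Two people reading the same scan could record different values, which would add avoidable disagreement between the investigator's ORR and ORR5.

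The marker clause is a different problem. It is a condition for CR that no planned measurement can satisfy. At stake are the CR category of best response and the duration of CR.

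**Working it through.** **1. The plan's own figure.** Protocol 10.3: ORR 45% vs 70%, 100 patients 1:1, 1-sided 5%. With the pooled-variance normal approximation, n = 50 per arm and mean rate 0.575:
- null SE = √(2 × 0.575 × 0.425 / 50) = 0.0989
- alternative SE = √((0.45 × 0.55 + 0.70 × 0.30) / 50) = 0.0957
- z = (0.25 − 1.645 × 0.0989) / 0.0957 = 0.91, so power is 81.9%. The stated figure of more than 80% reproduces.

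**2. All target lesions vanish, 5 mm entered for each.** With n lesions, the recorded fall is 1 − 5n/SLD. Each lesion was at least 10 mm, so SLD ≥ 10n and the fall is at least 50%. This is never SD, and target CR is met by disappearance anyway.

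**3. Only some vanish.** Let k lesions vanish from a baseline sum S, and let f be the fall with 0 mm entered. The fall with 5 mm entered is f − 5k/S. A PR becomes SD when 30% ≤ f < 30% + 5k/S.

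| Baseline (mm) | Later (mm) | 0 mm entered | 5 mm entered |
|---|---|---|---|
| 10 + 20 | gone + 18 | (18 − 30)/30 = -40.0%, PR | (23 − 30)/30 = -23.3%, SD |
| 20 + 40 | gone + 40 | (40 − 60)/60 = -33.3%, PR | (45 − 60)/60 = -25.0%, SD |
| 15 + 25 | gone + 25 | (25 − 40)/40 = -37.5%, PR | (30 − 40)/40 = -25.0%, SD |

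With one lesion gone, the window is 5/30 = 16.7 points wide at S = 30 mm, 8.3 points at 60 mm and 5 points at 100 mm.

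**4. The nadir.** Baseline 10 + 50 mm (SLD 60); then gone + 43, gone + 52, gone + 30.
- With 0 mm: 43 to 52 is +20.9% and +9 mm, so PD at the second visit. Leaving pseudoprogression handling aside, the SAP's response window closes there.
- With 5 mm: 48 to 57 is +18.8%, so no PD. The third visit is (35 − 60)/60 = -41.7%, PR.

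Here the 5 mm entry adds a responder and delays progression.

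**5. Tumor burden.** A single 10 mm lesion that vanishes is a target CR. If 5 mm is carried into the SAP 6.5.4.3 formula, the change is (5 − 10)/10 = -50%, and -100% cannot be reached.

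**6. What a loss of responders would cost.** The documents do not give the share affected. As an assumption, let the same share of responders in each arm move to SD:

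| Share | ORR, control / combination | Power |
|---|---|---|
| 0% | 45.0 / 70.0% | 81.9% |
| 2% | 44.1 / 68.6% | 80.3% |
| 5% | 42.8 / 66.5% | 77.7% |
| 10% | 40.5 / 63.0% | 73.3% |

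At 50 per arm, 2% of responders is 0.45 control patients (0.02 × 22.5) and 0.7 combination patients (0.02 × 35).

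**7. Non-target category, by elimination.** Take a patient with non-target disease at baseline, all lesions now gone, scans complete and no marker measured.
- CR: marker normalization cannot be shown.
- Non-CR/Non-PD: no lesion persists, and no marker is known to be above normal.
- PD: neither progression nor a new lesion.
- Not evaluable: every lesion was assessed.
- Not applicable: there were non-target lesions at baseline.
- Not done: the scans were performed.

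No category fits. The time-point table gives overall CR only for non-target CR, and PR if the non-target response is Non-CR/Non-PD or not evaluated.

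**The case against.** The 5 mm sentence is introduced for lesions that shrink over time, which most naturally describes a lesion that still has a diameter. Appendix D treats disappearance as a separate state, both in the CR definition and where it speaks of lesions that resolved and came back. SAP 6.5.4.3 does not mention 5 mm. The marker clause can be taken as surplus wording: nothing is measured, so it does not apply and the patient is a CR. Conventions may also sit in the Imaging Review Charter or the CRF instructions, which are not among the documents here.

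This much stands: the natural reading is available, and a sensible investigator may well use it. But it leaves the vanished lesion with no value at all, while the PR formula needs one. Appendix D is the text available to investigators, whose assessments decide the primary ORR. A charter convention for central readers alone would not settle what investigators record.

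Three stronger inferences are tempting and should be resisted:
- That complete disappearance cannot be scored. Target CR needs no SLD, and the marker clause does not reach patients without non-target lesions.
- That the 5 mm entry always removes responders. It lowers the chance of meeting the PR threshold at a given visit, but step 4 shows that the nadir can work the other way.
- That the marker clause turns every complete responder with non-target disease into a PR. Literally read, it leaves the patient unclassified; PR is one way of resolving that and CR is another.

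**Conclusion.** The two defects are real, separate and minor.

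The 5 mm rule, read literally, can score a PR as SD when some but not all target lesions clear, and occasionally shifts a patient the other way through the nadir. It is the only route to the primary ORR. It needs at least two target lesions, partial clearance and a fall inside the window in step 3, so the effect on ORR is probably small. The documents give no frequency, and the power range in step 6 is illustrative. It also assumes equal proportional losses in both arms; nothing in the documents shows a difference between arms. The percentage change in tumor burden is affected whenever a lesion clears and 5 mm is carried forward.

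The marker clause affects the CR category of best response and the duration of CR, for patients with non-target disease at baseline. It cannot turn a PR into SD, and ORR is unchanged as long as these patients are scored PR or CR.

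**What to change.** In Protocol Appendix D:
- record 0 mm for a target lesion that has disappeared, and keep 5 mm for one still visible but too small to measure;
- delete the tumor-marker clauses from the non-target CR and Non-CR/Non-PD definitions, or state that they do not apply because no marker is collected.

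Use the same recorded values in the tumor-burden formula of SAP 6.5.4.3 and in the independent review behind ORR5.

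The cost is a few sentences in Appendix D and a matching line in the CRF completion and imaging instructions. No new data or assessments are needed.
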